All randomized participants who underwent the surgical intervention (regardless of which technique was ultimately performed).

Protocol deviations will be prospectively classified as **major** (potentially affecting primary outcome validity) or **minor** (unlikely to affect outcomes) and documented in a deviation log.

SAP-3. BASELINE CHARACTERISTICS

Baseline characteristics will be summarized for the **ITT population** by treatment group:

Variable Type	Summary Statistic
Continuous, normally distributed	Mean ± Standard Deviation
Continuous, non-normal distribution	Median (Interquartile Range, IQR)
Categorical	n (%)

Normality of continuous variables will be assessed using both the **Kolmogorov-Smirnov test** and the **Shapiro-Wilk test**, complemented by visual inspection of Q-Q plots and histograms.

Variables to be summarized include: age, BMI at delivery, gestational age, parity, indication for cesarean section, type of anesthesia, skin incision type, uterine exteriorization status, pre-operative hemoglobin and hematocrit, and attending surgeon (anonymized).

No inferential statistics (p-values) will be calculated for baseline comparisons, as any imbalances in a randomized trial result from chance rather than systematic bias (CONSORT Statement 2010).

SAP-4. PRIMARY OUTCOME ANALYSIS

Outcomes:

1. **RMT** at 6–8 weeks and 6–7 months (continuous, mm)
2. **CSD prevalence** at 6–8 weeks and 6–7 months (binary)

SAP-4.1 RMT — Unadjusted Analysis

- **If normally distributed:** Independent samples **t-test** (or Welch's t-test if unequal variances)
- **If non-normally distributed: Mann-Whitney U test**

Reported statistics:

- Mean \pm SD (or Median [IQR]) per group
- Mean difference (MD) with 95% Confidence Interval
- Two-sided p-value (significance threshold: $\alpha = 0.05$)
- Effect size: Cohen's d (t-test) or rank-biserial correlation (Mann-Whitney)

SAP-4.2 RMT — Adjusted Analysis (Primary)

A **multiple linear regression model** will be constructed:

Dependent variable: RMT at 6–7 months

Independent variables:

- Treatment group (primary predictor)
- Age (continuous)
- BMI (continuous)
- Gestational age (continuous)
- Uterine exteriorization (yes/no)
- Surgeon experience level (senior/resident Year 4–5)
- Duration of labor before cesarean section (if applicable)
- Indication for cesarean section

Model assumptions verified:

- Linearity (partial regression plots)
- Homoscedasticity (Breusch-Pagan test)

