- Independence of residuals (Durbin-Watson test)

- Absence of multicollinearity (Variance Inflation Factor < 5)
- Normality of residuals (Shapiro-Wilk on residuals)

Reported: Adjusted MD (β coefficient) with 95% CI, R^2 , adjusted R^2 , F-statistic, overall model p-value

SAP-4.3 CSD Prevalence — Analysis

Unadjusted:

- Chi-square test or Fisher's exact test (if expected cell count < 5)
- Relative Risk (RR) with 95% CI
- Absolute Risk Reduction (ARR) and Number Needed to Treat/Harm (NNT/NNH)

Adjusted:

- **Binary logistic regression** at 6–8 weeks and at 6–7 months
- Covariates: same set as RMT regression model
- Variables with $p < 0.20$ in univariate analysis AND a priori confounders (age, parity, BMI, indication) included
- Model fit: **Hosmer-Lemeshow test**
- Multicollinearity: **Variance Inflation Factors (VIF)**
- Discrimination: **Area Under the ROC Curve (AUC)**
- Results expressed as adjusted **Odds Ratios (OR)** with 95% CI

SAP-5. SECONDARY OUTCOME ANALYSES

SAP-5.1 Continuous Secondary Outcomes

- Unadjusted: t-test or Mann-Whitney U as appropriate
- Adjusted: Multiple linear regression (same covariate set)
- Results: Mean difference or median difference with 95% CI

SAP-5.2 Binary Secondary Outcomes (Complications, Transfusion)

- Unadjusted: Chi-square or Fisher's exact test
- Results: RR, ARR, NNT/NNH with 95% CI

SAP-5.3 CSD Morphological Dimensions

Analyzed within the **CSD-positive subgroup only**:

- Depth, length, width: Mann-Whitney U test
- **CSD Volume** (ellipsoid formula): Mann-Whitney U test

SAP-5.4 Repeated Measures — RMT at 6 Weeks and 6 Months

Method: Linear Mixed-Effects Model (LME)

Model structure:

- Fixed effects: treatment group, time point (6 weeks vs. 6 months), treatment × time interaction
- Random effect: participant-level intercept (accounts for within-subject correlation)
- Covariance structure: Unstructured (preferred); compound symmetry if convergence issues

Interpretation:

- Significant interaction ($p < 0.05$): treatment effect differs across time points
- Non-significant interaction: main effects interpreted independently

SAP-5.5 Symptom Outcomes (Ordinal / Binary)

- Binary symptoms (spotting, dyspareunia): Chi-square or Fisher's exact test; RR with 95% CI
- **Paired temporal evolution** (6 weeks → 6 months within each group): **McNemar's test**
- Adjusted: Binary logistic regression

SAP-5.6 Hemoglobin Variation and Blood Loss

- ΔHb : t-test or Mann-Whitney U; mean difference with 95% CI

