Type of cesarean section	Scheduled vs. Intrapartum	Interaction term
Surgeon category	Senior vs. Resident Year 4–5	Interaction term

Test for interaction: Likelihood ratio test comparing models with and without the interaction term.

All subgroup analyses are exploratory and hypothesis-generating. No correction for multiple comparisons is applied to subgroup analyses; results will not drive primary conclusions.

Results will be presented in **forest plots**.

SAP-8. SENSITIVITY ANALYSES

Analysis	Method
SA-1: Per-Protocol population	Repeat primary analysis in PP population
SA-2: Intraoperative complication exclusion	Exclude participants with major intraoperative events (corporeal hysterotomy, hysterotomy extension > 2 cm)
SA-3: Multiple imputation for missing RMT	MICE — 5 scenarios: observed data, LOCF, best case, worst case, 6-week status carry-forward
SA-4: Inverse Probability Weighting (IPW)	Adjust for informative loss to follow-up
SA-5: Binary threshold analysis	Proportion with RMT < 2.5 mm and RMT < 3.0 mm; Chi-square test
SA-6: Complete case analysis	For comparison with imputed results

SAP-9. MULTIPLICITY AND TYPE I ERROR CONTROL

- **Primary outcomes:** $\alpha = 0.05$, two-sided, for each co-primary endpoint (RMT and CSD prevalence at 6 weeks and 6 months)
- **Secondary outcomes:** Exploratory; **Holm-Bonferroni correction** applied to control family-wise error rate
- **Unmeasured confounders:** **E-value** calculated to quantify the minimum strength of an unmeasured confounder needed to explain away observed associations

SAP-10. MISSING DATA STRATEGY

Data Type	Strategy
Primary outcome (RMT at 6 months)	Five imputation scenarios (MICE)
Secondary continuous outcomes	Complete case + sensitivity with imputation if > 10% missing
Binary outcomes	Complete case analysis

Symptom questionnaires	Linear mixed model (full information maximum likelihood)
------------------------	--

Missing data mechanism assessed by **Little's MCAR test**.

Participants lost to follow-up compared to completers on key baseline variables; reasons for dropout documented and reported.

SAP-11. PRESENTATION OF RESULTS

Results reported in accordance with **CONSORT 2010** guidelines:

- **Table 1:** Baseline characteristics (ITT population) — no p-values
- **Figure 1:** CONSORT flow diagram
- **Table 2:** Primary and secondary outcomes with between-group comparisons
- **Table 3:** Subgroup analysis (forest plots)
- **Table 4:** Multivariate analysis results

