- **Table 5:** Safety and adverse event summary
- **Figure 2:** Bland-Altman plot for RMT reproducibility
- **Figure 3:** ROC curve for predictive model

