9.2 Secondary Outcomes

Ultrasonographic outcomes:

- CSD morphological dimensions: depth, length, width (mm)
- CSD volume: estimated by ellipsoid formula — $V \text{ (mm}^3\text{)} = (\pi/6) \times \text{Length} \times \text{Width} \times \text{Depth}$
- **Adjacent Myometrial Thickness (AMT)**: measured 5–10 mm from the scar on both sides (mm)
- **Myometrial Ratio (RM)**: calculated as $\text{RM (\%)} = \text{RMT} / \text{AMT} \times 100$
- Uterine position (anteverted / retroverted)

Intraoperative outcomes:

- **Hysterorrhaphy duration** (minutes and seconds)
- **Total operative time** (minutes and seconds)
- **Visually Estimated Blood Loss (PSTEV)**: volume of bloody fluid in suction canister at end of surgery, minus estimated amniotic fluid volume (mL)
- **Calculated Total Blood Loss (PSTC)**:

$$PSTC(mL) = \frac{VST \times (Hct_{preop} - Hct_{postop})}{35} \times 100 + \text{Compensated losses}$$

Where: VST (Total Blood Volume) = Pre-pregnancy weight (kg) \times 65 \times 1.4;
Compensated losses = Number of packed red blood cell units transfused \times 500 mL; 35 = reference hematocrit of one packed RBC unit

- Number of **additional hemostatic sutures**
- **Intraoperative complications**: hysterotomy extension, ureteral injury, bladder injury, intestinal injury, hemorrhage requiring transfusion

Immediate postoperative outcomes:

- **Hemoglobin variation**: $\Delta\text{Hb (g/dL)} = \text{Hb preoperative} - \text{Hb at Day 1 postpartum}$
- **Transfusion requirement** (packed RBC units)
- **Early postoperative complications**: postpartum endometritis, surgical site infection, parietal hematoma, surgical revision, thromboembolic events

- **Hospital length of stay (days)**

Medium-term symptom outcomes (at 6–8 weeks and 6–7 months):

- Postmenstrual spotting (characteristic of CSD)
- Prolonged menstruation (> 7 days)
- Dysmenorrhea requiring medication
- Chronic pelvic pain (outside menstruation)
- Menometrorrhagia
- Dyspareunia

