11. MULTIPLICITY CONTROL

- Primary outcomes: $\alpha = 0.05$, two-sided
- Secondary outcomes: **Holm-Bonferroni correction**
- Unmeasured confounders: **E-value** reported for primary associations

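### Complications and transfusion are not exempt from the Holm-Bonferroni correction on secondary outcomes, and no rule says whether the corrected test or the 95% CI governs

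*SAP*

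**What the plan says.** SAP-9 treats secondary outcomes as "Exploratory; Holm-Bonferroni correction applied to control family-wise error rate". Section 11 of the combined document has "Secondary outcomes: Holm-Bonferroni correction". Neither place lists the members of the family, gives its size, or makes an exception for safety.

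Harms belong to that class by name. One SAP section is titled "SAP-5.2 Binary Secondary Outcomes (Complications, Transfusion)". Protocol 9.2 lists five intraoperative complications, transfusion, and five early postoperative complications ("postpartum endometritis, surgical site infection, parietal hematoma, surgical revision, thromboembolic events") under the same secondary-outcome heading as niche dimensions, AMT, operative times, blood loss and symptoms.

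For these outcomes SAP-5.2 plans "Unadjusted: Chi-square or Fisher's exact test" and "Results: RR, ARR, NNT/NNH with 95% CI". Section 7.3 of the combined document plans the same kind of estimates. Neither says that the intervals are adjusted for multiplicity.

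SAP-2.3 defines a safety population: "All randomized participants who underwent the surgical intervention (regardless of which technique was ultimately performed)". SAP-11 lists a Table 5, "Safety and adverse event summary", without describing its content. No analysis is explicitly assigned to the safety population, and no passage says how the safety results are to be interpreted.

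**The concern.** Family-wise control limits false positive claims. For harms the costlier error is usually the missed one, and here the bar for a harm depends on how many unrelated ultrasound and symptom outcomes the trial happens to measure. The plan is also uneven: SAP-9 tests each co-primary endpoint at 0.05, and SAP-7 leaves subgroups uncorrected, while a complication would first have to pass about 0.05/38.

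The same harm would also be reported in two ways, by a Holm-corrected test and by an ordinary 95% CI. The two can disagree, and the plan does not say which one carries the safety conclusion. A non-significant corrected p-value could then be taken as reassurance although the test had little chance of detecting a relevant excess.

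**Working it through.** **The plan's own figure.** Protocol section 11 sizes the trial on RMT at 6 months: n = 2 × (1.96 + 0.842)² × 3.5² / 1.3² = 113.8, so 114 per group, and 114 / 0.70 = 162.9, so 163. Both reproduce. Enrolment is 192 per group. No figure is given for complication rates, for power on complications, or for the size of the Holm family.

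**Size of the family, counted from protocol 9.2 at its scheduled visits.**
- Niche depth, length, width, volume: 4
- AMT and myometrial ratio at two visits: 4
- Hysterorrhaphy duration, operative time, two blood-loss measures, additional sutures: 5
- Intraoperative complications: 5
- Hemoglobin change and transfusion: 2
- Early postoperative complications: 5
- Length of stay: 1
- Six symptoms at two visits: 12

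Total: 4 + 4 + 5 + 5 + 2 + 5 + 1 + 12 = 38. The harm items alone number 5 + 5 + 1 = 11. The family-wise level is taken as 0.05, which the documents state only for the primary outcomes and the sample size. The first Holm threshold is then 0.05/38 = 0.0013.

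**Chance that a true difference is declared non-significant.** Two-sided chi-square test, 192 per arm, exact enumeration of both binomial counts. The event rates are assumptions.

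| True rates | No correction (0.05) | 11 tests | 20 tests | 38 tests | 50 tests |
|---|---|---|---|---|---|
| 5% vs 10% | 53% | 84% | 89% | 92% | 94% |
| 2% vs 6% | 47% | 82% | 87% | 91% | 94% |
| 5% vs 15% | 8% | 32% | 39% | 47.5% | 51% |

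For 5% vs 10% with 38 tests, the correction adds 92 − 53 = 39 points. The remaining 53 points are there without it. At 80% power that comparison would need 435 per group at 0.05 and 911 at 0.05/38.

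**Does the step-down rescue it?** Holm loosens as other hypotheses are rejected. In 200,000 simulated trials with 38 tests, power for 5% vs 10% was 7.7% with no other true effects, 8.3% with 5 strong effects elsewhere, 9.2% with 10 and 12.2% with 20. The first-step figure is therefore a fair summary.

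**Can the interval and the corrected test disagree?** Take 10/192 vs 24/192 events.
- RR = 24/10 = 2.40. SE of log RR = √(1/10 − 1/192 + 1/24 − 1/192) = 0.362. The 95% CI is 2.40 × exp(±1.96 × 0.362) = 1.18 to 4.88.
- Risk difference = 14/192 = 7.3 points, 95% CI 1.7 to 12.9.
- Pooled rate 34/384, z = 2.51, raw p = 0.0119.
- First-step Holm p = 38 × 0.0119 = 0.45.

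The interval excludes 1 while the corrected test is far from significant. To reach significance the multiplier would have to fall to 0.05/0.0119 = 4.2 or less, so at least 34 of the other 37 outcomes would have to be rejected first.

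**The case against.** A reader might infer that the safety comparison is bound to look clean, or that the corrected test is the plan's only safety rule. The documents do not support either. SAP-5.2 and section 7.3 of the combined document require RR, ARR and NNT (with NNH in SAP-5.2), with 95% CIs. An observed 5% vs 10% would be reported as RR 2.0 (about 0.95 to 4.23), whatever the Holm p-value. The SAP calls secondary outcomes exploratory, plans a separate safety table, and nowhere equates non-significance with safety. It has no safety decision rule at all.

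Nor can the 92% be laid wholly on Holm, because more than half of it reflects a trial sized on RMT. The protocol defines no composite complication endpoint, and for single items at an assumed 1% to 2%, power for a doubling is only 12% to 21% uncorrected (normal approximation). Removing the correction would leave those comparisons uninformative. The family of 38 is a count from protocol 9.2, not a figure in either SAP.

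Finally, both arms are closures in current practice and comparing complications is a stated secondary objective. An excess in one arm is an advantage claimed for the other, so controlling false claims in both directions is defensible.

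All of this stands as a limit on the point. It does not remove it. The exploratory label sits in the same line as the family-wise correction, so it does not lift the correction from harms. The planned intervals make the missing rule matter more, because they can contradict the corrected test.

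**Conclusion.** The point holds in a limited form. As written, both SAPs correct harms together with unrelated secondary outcomes, in a family that is never listed, and do not say whether the corrected test or the interval governs. With 192 per arm and 38 tests, the correction raises the chance of a non-significant result from 53% to about 92% for 5% vs 10%, and from 8% to about 47.5% for 5% vs 15%. The second pair shows the effect of Holm most clearly, since the uncorrected comparison is well powered.

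These figures rest on assumed event rates, a family-wise level of 0.05 and the count of 38. The count is not critical: 20 to 50 tests give 89% to 94% for the doubling, and the 11 harm items alone give 84%. It would go too far to say that harms are hidden, since the estimates and intervals remain visible. This should be corrected, but the trial's primary conclusions do not depend on it.

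**What to change.** In SAP-9 and in section 11 of the combined document, list the Holm-Bonferroni family and limit it to the non-safety secondary outcomes. Exclude intraoperative and early postoperative complications, transfusion and surgical revision.

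State that each harm is reported in the safety population with the risk difference and RR already planned and unadjusted 95% CIs, that safety is read from those intervals, and that a non-significant p-value is not evidence of equal safety.

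The change is to wording only and needs no new data. It should be made before the unblinded analysis. The cost is a higher chance of a false harm signal, in either direction between two active techniques. That is the usual choice for safety outcomes, and the intervals keep the uncertainty in view. The change does not cure the low power for rare single complications, and the report should say so.

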7.4 Paired Temporal Symptom Evolution

McNemar's test (within-group: 6 weeks \rightarrow 6 months)

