12. MISSING DATA

Little's MCAR test to assess missing data mechanism.

Outcome	Strategy
RMT at 6 months	Five-scenario MICE (SA-3)
Secondary continuous	Complete case + MICE if > 10% missing
Binary outcomes	Complete case
Symptom questionnaires	Full information maximum likelihood (FIML) via mixed models

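### SAP-10 handles missing symptom answers with a mixed model, but SAP-5.5 names only tests that drop women with no 6-month answer

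*SAP*

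**What the plan says.** SAP-10 gives symptom questionnaires their own row in the missing-data table: "Linear mixed model (full information maximum likelihood"). The row for binary outcomes reads "Complete case analysis". Section 12 of the SAP bound with the protocol has the same two rows, but its symptom entry is "Full information maximum likelihood (FIML) via mixed models", without the word linear.

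The symptom analyses are set out under "SAP-5.5 Symptom Outcomes (Ordinal / Binary"). The between-arm comparison is "Binary symptoms (spotting, dyspareunia): Chi-square or Fisher's exact test; RR with 95% CI". Change from 6 weeks to 6 months within each arm is tested by McNemar's test (section 7.4 of the bound SAP: "McNemar's test (within-group: 6 weeks"), and the adjusted analysis is binary logistic regression. SAP-5.5 contains no mixed model. The only one SAP-5 specifies is in SAP-5.4, for RMT.

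Protocol section 9.2 lists six symptoms at both follow-up visits. Section 11 anticipates 30% loss to follow-up and gives 192 women enrolled per group.

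**The concern.** Take a woman who answers the questionnaire at 6 weeks and does not come back. Under SAP-5.5 she is absent from the 6-month comparison. Under SAP-10 her 6-week answer informs it. Both are current instructions for the same outcome, and neither document says which one produces the reported result. For the symptom mixed model no link function, fixed effects, covariance structure or target quantity is given.

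SAP-1 says the plan exists to limit post-hoc analytical decisions, and this leaves one open. It matters most if women with symptoms are more, or less, likely to return, because a complete-case comparison then rests on a selected group. The symptoms are the trial's patient-reported evidence on whether a scar defect has consequences.

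**Working it through.** **1. Can the SAP-5.5 methods carry out the SAP-10 rule?** Chi-square, Fisher and logistic regression at 6 months need the 6-month answer, and McNemar needs both answers. None uses a 6-week answer on its own, so likelihood-based handling of missing answers cannot operate through them. A linear mixed model can use it, but on 0/1 data it yields a risk difference, not the risk ratio in SAP-5.5 or the odds ratio from its logistic model.

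**2. How many women are affected?** 192 × 0.30 = 57.6, or up to about 58 per arm. This is an upper bound: a woman who also misses 6 weeks contributes under neither rule, and the documents do not split the 30% by visit.

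**3. How far can the results differ?** The documents give no symptom rates, so these are assumed. The 6-week prevalence is 30% in arm 1 and 20% in arm 2. The 6-month risk is 60% if symptomatic at 6 weeks and 10% if not. Loss is 30% overall in each arm.

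True 6-month risks:
- arm 1: 0.30 × 0.60 + 0.70 × 0.10 = 0.25
- arm 2: 0.20 × 0.60 + 0.80 × 0.10 = 0.20
- risk difference 5.0 points, risk ratio 1.25

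The complete-case risk in an arm is (r1 × 0.60 + r0 × 0.10) / (r1 + r0). Here r1 and r0 are the fractions of the arm that return with and without 6-week symptoms, and r1 + r0 = 0.70.

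- Symptomatic women mostly stay (10% of them lost). Arm 1: r1 = 0.30 × 0.90 = 0.27, r0 = 0.43, risk = 0.205/0.70 = 29.3%. Arm 2: r1 = 0.18, r0 = 0.52, risk = 0.160/0.70 = 22.9%.
- Symptomatic women often leave (50% of them lost). Arm 1: r1 = 0.15, r0 = 0.55, risk = 0.145/0.70 = 20.7%. Arm 2: r1 = 0.10, r0 = 0.60, risk = 0.120/0.70 = 17.1%.

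| Loss pattern | Complete-case risk difference (points) | Complete-case risk ratio |
|---|---|---|
| Unrelated to symptoms | 5.0 | 1.25 |
| Symptomatic stay, both arms | 6.4 | 1.28 |
| Symptomatic leave, both arms | 3.6 | 1.21 |
| Leave in arm 1, stay in arm 2 | −2.1 | 0.91 |
| Stay in arm 1, leave in arm 2 | 12.1 | 1.71 |

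**4. What would the mixed model give?** In 200 simulated trials per pattern (192 per arm, all but the third row), a random-intercept linear mixed model averaged 4.5 to 5.1 points. It and the complete-case chi-square test fell on different sides of p = 0.05 in 8.5% of trials with unrelated loss, 9% when symptomatic women stayed in both arms, and 18% and 45.5% under the two opposite patterns.

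**5. Does a logistic mixed model work with only two visits?** I fitted one by quadrature (101 nodes) to the expected counts of each row and averaged over the random intercept. The 6-month risk difference was 4.9 to 5.1 points and the risk ratio 1.24 to 1.25 in all five rows.

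**The case against.** **The two SAP-10 rows need not clash.** It is tempting to say that the binary row and the symptom row give contradictory rules for the same variables. The SAP does not support that firmly. SAP-5.2 ties its binary secondary outcomes to complications and transfusion, and SAP-5.5 treats symptoms apart, so the symptom row can be read as the specific one. This stands. The clash that remains is between SAP-10 and SAP-5.5.

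**Not every item is shown to be yes/no.** A reader might infer from the list in section 9.2 that all six are. The questionnaire is not in the documents, the SAP-5.5 heading allows ordinal items, and only spotting and dyspareunia are named as binary. This stands, and the fix has to cover both scales.

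**A linear mixed model on 0/1 data is not unusable.** It estimates a risk difference and recovered it well in step 4. The valid complaint is that it does not produce the measures SAP-5.5 leads to.

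**Large shifts need opposite loss patterns by arm.** Participants are blinded, which makes that less likely. With the same pattern in both arms the complete-case result moves by about 1.4 points in step 3. This stands and limits the size of the point.

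**Other parts of the plan touch the issue.** SA-4 applies inverse probability weighting for informative loss, but SAP-8 does not tie it to symptoms. Protocol section 5.3 lists loss to follow-up as a post-randomisation exclusion. That does not settle the matter: the bound SAP takes precedence for analysis and keeps all randomised women in its primary population.

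**Conclusion.** The inconsistency is real in the current text of the SAP: its missing-data section names a method that its symptom section never specifies and cannot carry out. Up to about 58 of 192 women per arm are counted or not according to which section is followed.

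A reader might infer that the 6-month symptom result is therefore biased. The documents do not show that. If loss is unrelated to 6-week symptoms the two approaches agree on average, though they can differ in a single trial. If the relation is the same in both arms the shift is small (5.0 to 6.4 or 3.6 points at the assumed rates). Only opposite patterns by arm produced a material change (to −2.1 or 12.1). All these sizes rest on assumed prevalences and loss rates, and on loss depending only on arm and the 6-week answer.

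Symptoms are secondary and labelled exploratory in SAP-9, so the RMT and CSD conclusions do not depend on this. It should be corrected before analysis, but it does not threaten the trial's main result.

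**What to change.** State one rule for symptoms in SAP-5.5, SAP-10 and section 12 of the bound SAP:

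- For each yes/no symptom, fit a logistic mixed model with a random participant intercept and terms for arm, visit and arm × visit, using all 6-week and 6-month answers. Standardise the 6–7-month arm contrast to a marginal risk ratio and risk difference.
- Fit it by adaptive Gauss-Hermite quadrature, with the number of points stated, and not by the Laplace approximation. With two visits per woman, Laplace fits at the assumed rates were unstable: in one test dataset the 6-month risk difference moved from −4.4 to +0.3 points with the starting values.
- Use the ordinal-logit equivalent for any item recorded on an ordinal scale.
- Say that the complete-case row for binary outcomes does not cover symptoms. Keep complete-case chi-square or Fisher as a sensitivity analysis.
- If the model does not converge, impute the 6-month answer from arm and 6-week answer by multiple imputation. Falling back to complete case would let the data choose the missing-data rule symptom by symptom.

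The cost is SAP wording and a little more analysis work, with no new data or visits. The packages lme4 and mice are already listed in section 13 of the bound SAP; an ordinal mixed model would need one that is not. Estimates for rare symptoms may be unstable.
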